### Analysis of between-group changes

Three measurement points will be available for analysis. Baseline (i.e., before randomization), post-treatment (post; i.e., immediately after treatment), and 3-month follow-up (3mfu) after post-treatment. The 3-month follow-up is the pre-determined primary endpoint. To utilize all available data, all three measurement points from all randomized patients will be included in the analysis. The model will include group, time, and group-by-time interaction effect as fixed effects. Time will be entered as a factor/categorical variable with three levels, baseline, post, and 3mfu, with baseline as the reference category. Thus, the model estimates separate interaction effects for post and 3mfu, allowing us to investigate the relative change from baseline between the groups at both post and 3mfu. Inference about treatment effect at the primary endpoint will be based on the p-value of the group-by-3mfu interaction effect, at a significance alpha-level of .05. The mixed models will also include a random intercept to account for the within-individual dependence between the individual observations over time.

Between group effect sizes (Cohen's d) will be calculated as the interaction effects (group-by-post and group-by-3mfu) divided by the baseline standard deviation for the respective measure. To obtain 95% confidence intervals for the effect sizes, we will bootstrap the mixed models analysis 5,000 times. The bootstrap sampling will be performed at the individual level, i.e., each sample included a random sampling (with replacement) of all randomized individuals. Each time an individual is selected, all their observations will be included with a new clustering identifier. For each bootstrap sample, the mixed models will rerun to obtain the interaction effects and the baseline standard deviation will be recalculated to obtain the post and 3mfu effect sizes. The 5,000 bootstrapped effect sizes are then used to obtain bias-corrected and accelerated 95% confidence intervals.

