### Analysis of within-group changes in the MI-CBT group

These analyses will be performed to investigate the long-term changes in the MI-CBT group compared to baseline. One long-term follow-up measurement points will be available at this point, 12 months after post-treatment (12mfu). To utilize all available data, we will also include the baseline, post, and 3mfu measurement points in the mixed-models analysis. Time will be entered as a factor/categorical variable with four levels, baseline, post, 3mfu, and 12mfu, with baseline as the reference category. Thus, the model estimated separate effects of time for post, 3mfu and 12mfu, allowing us to investigate the change from baseline in the MI-CBT group. The mixed models will also include a random intercept to account for the within-individual dependence between the individual observations over time.

Within-group effect sizes will be calculated by dividing the time effects by the baseline standard deviation and 95% confidence intervals are obtained by the same bootstrapping method used for the between-group effects.

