### Analysis of healthcare consumption

Regarding healthcare consumption data (i.e., the number of healthcare visits during the last three months), we expect that the distribution of scores will not be suitable for a linear mixed model as described above, since number of healthcare visits is a count variable. If appropriate, we will use statistical a model more suitable for skewed count data, generalized mixed model using the Poisson distribution with a log link function random intercept. Confidence intervals for fixed effects will be calculated based on the guidelines provided at <https://stat.ethz.ch/pipermail/r-sig-mixed models/2011q1/015910.html>. Effect sizes will not be calculated for this data and instead we will exponentiate the group-by-time interaction effects (between-groups analyses) and Time effects (within-group analyses) to get the percentage reduction in healthcare consumption. In other respects, between- and within group analyses will be performed with the same model specifications as the continuous outcomes.

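### Does the healthcare consumption analysis mistake an exponentiated Poisson coefficient for a percentage reduction?

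*SAP*

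**What the plan says.** The outcome is a count, "the number of healthcare visits during the last three months". If appropriate, it is to be analysed with a "generalized mixed model using the Poisson distribution with a log link function random intercept". Standardised effect sizes are dropped for this outcome. In their place, the SAP says, "we will exponentiate the group-by-time interaction effects (between-groups analyses) and Time effects (within-group analyses) to get the percentage reduction in healthcare consumption". Confidence intervals are planned for the fixed effects, without naming a scale.

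The rest is borrowed from the linear models: "between- and within group analyses will be performed with the same model specifications as the continuous outcomes". For the between-group analysis this means "The model will include group, time, and group-by-time interaction effect as fixed effects", with time coded "with three levels, baseline, post, and 3mfu, with baseline as the reference category". For the within-group analysis of the MI-CBT arm, time is coded "with four levels, baseline, post, 3mfu, and 12mfu, with baseline as the reference category". The SAP does not state the reference level for group.

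**The concern.** With a log link, exponentiating a coefficient gives a ratio, and a ratio of 0.80 is a 20% reduction, not an 80% one. The SAP goes from exponentiation to percentage reduction in one sentence without the subtraction. It also uses one phrase for two quantities: the change from baseline within MI-CBT, and the difference between the groups' changes from baseline. The second can favour MI-CBT even if that arm's consumption never fell.

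The exponentiated coefficients are the only effect measure planned in place of effect sizes for this outcome. If they were reported directly as reductions, the published figure would be wrong at every value except 0.50. If the interaction were described as a fall in consumption, readers could be misled about what happened in the treated arm.

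**Working it through.** The SAP gives no numerical result here, so there is no figure to reproduce. The check is the algebra of the stated model, illustrated with assumed rates.

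**Inputs from the SAP.** Log link, Poisson distribution and random intercept (Analysis of healthcare consumption). Group, categorical time and their interaction, with baseline as reference (Analysis of between-group changes). Time only, with baseline as reference (Analysis of within-group changes in the MI-CBT group). The recall window is a fixed three months, so counts can be read as rates without an offset.

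**Model.** log E[Y] = b0 + b1·group + b2·time + b3·group·time + u, taking the comparator as the reference group (an assumption).

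- Within-group model: exp(time effect) = follow-up rate ÷ baseline rate.
- Between-group model: exp(b3) = (follow-up ÷ baseline in MI-CBT) ÷ (follow-up ÷ baseline in the comparator).
- The random intercept u cancels from both ratios.

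**Conversion.** Percentage reduction = 100 × (1 − exp(b)). Ratios are assumed.

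| exp(b) | 100 × (1 − exp(b)) | 100 × exp(b), the literal misreading |
|---|---|---|
| 0.50 | 50 | 50 |
| 0.70 | 30 | 70 |
| 0.80 | 20 | 80 |
| 0.90 | 10 | 90 |
| 1.00 | 0 | 100 |
| 1.20 | −20 (an increase) | 120 |

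The misreading gives itself away: no effect would appear as the abolition of all healthcare visits, and an increase as a reduction of more than 100%.

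**Interval.** With assumed b = ln(0.80) = −0.2231 and SE = 0.105, the ratio limits are exp(−0.2231 − 1.96 × 0.105) = 0.651 and exp(−0.2231 + 1.96 × 0.105) = 0.983. The same conversion gives 100 × (1 − 0.983) = 1.7% and 100 × (1 − 0.651) = 34.9%. The limits swap places, and nothing else changes.

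**The interaction label.** Two sets of assumed mean visits:

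- MI-CBT 4.0 to 2.4, comparator 4.0 to 3.0: exp(b3) = 0.60 ÷ 0.75 = 0.80. The arms' own reductions are 40% and 25%.
- MI-CBT 4.0 to 4.0, comparator 4.0 to 5.0: exp(b3) = 1.00 ÷ 1.25 = 0.80. MI-CBT did not fall at all.

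In both cases 1 − exp(b3) = 20%. This is a reduction relative to what MI-CBT would have shown had it followed the comparator's change. In the first, 4.0 × 0.75 = 3.0 expected against 2.4 observed, and 1 − 2.4/3.0 = 20%. In the second, 4.0 × 1.25 = 5.0 expected against 4.0 observed, and 1 − 4.0/5.0 = 20%.

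**Simulation.** A Poisson regression fitted to simulated counts with person-level random intercepts, using the first set of rates, gave exp(time) = 0.750 for the comparator and exp(interaction) = 0.801, as the algebra predicts.

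**The case for a change.** The best argument for a correction is that supplying the subtraction repairs only the time effects. For the interaction, 1 − exp(b3) is a relative difference between two changes and need not be a reduction in either arm, as the second set of rates shows. A plan that makes this quantity its effect measure ought to name it correctly, and one or two sentences would do so.

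Part of this stands: one phrase for both contrasts is loose. But the SAP marks the interaction as the between-group result and the time effect as the within-group result, and the two preceding sections define those contrasts as relative change between groups and change from baseline in MI-CBT. A reader of the three sections knows what each coefficient compares. A percentage derived from a between-group contrast is ordinarily read as relative to the comparator, and on that reading the 20% above is correct.

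A tidier sentence would also have to fix something the SAP leaves open. Naming the comparator's change as the denominator presumes that the comparator is the reference level for group. With the opposite coding the ratio inverts (0.80 becomes 1/0.80 = 1.25). Analysts settle this when they report the direction of the effect.

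**Conclusion.** The observation is accurate, but no change follows. The SAP leaves out the routine step from a ratio to a percentage and uses one loose label for two contrasts that it distinguishes elsewhere. The fitted model, the interaction test, its p-value and the intervals for the coefficients are identical whether or not the step is written down. Any ratio can be recovered from a reported coefficient and its interval.

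The harm would require an analyst to report an unconverted ratio as a reduction and not notice that a null effect then reads as 100%. The size for this trial cannot be stated, because the SAP gives no ratios and every figure above is assumed. The conclusion rests on two assumptions: that the analysts apply 100 × (1 − exp(b)) to the estimates and their limits, and that they describe the interaction as relative to the comparator. Both are ordinary practice for a log-link model.

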### Analysis of accelerometer data of physical activity and sleep

Regarding accelerometer data, each participant will contribute with values at the three timepoints (baseline, post, 3mfu). Data from the accelerometer (ActiGraph wGT3x-BT) will be processed as previously described (1) using appropriate thresholds to define different levels of intensity (e.g., Moderate-to-vigorous physical activity, MVPA). Daily average MVPA will be calculated as the weighted mean of weekdays and weekend days, that is,  $\{([mean\ of\ weekdays \times 5] + [mean\ of\ weekend\ days \times 2])/7\}$ . Data processing will be conducted by means of the software program R and the package GGIR.

### Blood sample analysis

The blood samples are collected at three timepoints: pre-treatment, post-treatment and at the 3mfu. Regarding blood samples, descriptive statics and changes over time using appropriate (i.e., based on distribution) repeated measures statistics will be performed. Venous blood is collected for local analyses of fasting plasma glucose, HbA1c, plasma total cholesterol, LDL, HDL, triglycerides, hsCRP, creatinine.

